3.2.6 Last Value on BRV Treatment

Last Value for QOLIE-31-P, HADS, EQ-5D, and socio-professional data is the last assessment strictly after the date of first dose of BRV and up to and including the YEV at the end of the second year and any EDVs for subjects who did not complete through the YEV at the end of the second year.

Last Value for clinical laboratory parameters, vital signs, and ECGs is the last available result obtained after the first dose of BRV and prior to or on the date of last dose of BRV. All

scheduled and unscheduled assessments within this time period will be considered. Last Value will be determined separately for each laboratory parameter.

3.2.7 Exposure duration and exposure duration cohorts

At the final analysis, the overall duration of exposure (or On Treatment Period) will be calculated as the date of last dose of BRV minus the date of first dose of BRV plus 1 day. Each subject will be classified into one or more of the following exposure duration cohorts based on the duration of BRV exposure as calculated above:

All subjects	≥1 day
≥3 months	≥90 days
≥6 months	≥180 days
≥12 months	≥360 days

This categorization will continue in 6-month increments past 12 months up to a time point that will be determined based on cumulative exposure at the time of the database lock.

3.2.8 Study visit cohorts

Study visit cohorts are defined for summaries of QOLIE-31-P, HADS, and EQ-5D. Six-month, 12-month, 18-month, and 24-month cohorts are defined. Subjects will be classified into a study visit cohort if they attend the scheduled visit at the time point defined by the cohort. For example, subjects will be included in the 18-month study visit cohort if they attend the scheduled visit at 18 months (ie, FEV at Month 18). Subjects may be classified in more than 1 cohort. Generally, subjects included in a cohort for a later visit will be included in all earlier study visit cohorts (eg, 6-month and 12-month study visit cohorts for subjects in the 18-month study visit cohort), although this may not be the case in the event of a missed visit or if an unscheduled visit is conducted in lieu of a scheduled visit.

3.3 Definition of Baseline Values

Baseline for all study outcomes will be based on baseline from the previous studies. For assessments performed at scheduled and unscheduled visits, Baseline will generally be the last result obtained or prior to the randomization visit of the previous study. Baseline will be defined separately for each hematology, blood chemistry, and urinalysis parameter.

Baseline for the evaluation of seizure frequency and seizure days will be calculated from the core study seizure diary based on the rules defined in Section 3.8.1 .

3.4 Protocol deviations

The criteria for identifying important protocol deviations and the classification of important protocol deviations will be defined separately in the Specification of Protocol Deviations document. Whenever possible, criteria for identifying important protocol deviations will be implemented algorithmically to ensure consistency in the classification of important protocol deviations across all subjects.

3.5 Analysis Sets

3.5.1 Safety Analysis Set

The Safety Analysis Set will consist of all subjects who took at least 1 dose of study drug but not including subjects entering the study from N01315.

Summaries of demographics and baseline characteristics, medical history, AEDs, non-AEDs, HADS, study drug exposure, and safety outcomes will be provided for the Safety Analysis Set.

A Modified Safety Analysis Set will also be defined to consist of all subjects who took at least 1 dose of study drug including subjects entering the study from N01315. Demographic, ongoing medication and safety assessment listings will be provided based on the Modified Safety Analysis Set.

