13. STATISTICS

A general description of statistical methods is presented below. Additional detail will be described in the Statistical Analysis Plan (SAP). Statistical analyses of data for subjects transferring from N01315 will be handled as described in the SAP.

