13.1 Statistical and Analytical Plans

13.1.1 Study Population(s)

- Subpopulations

There are 3 mutually exclusive subpopulations. They are defined based upon enrollment.

1. Partial onset seizure: Subjects enrolled from prior studies N01114, N01252, and subjects from N01254 with a diagnosis of POS at N01254 study entry
2. Primary generalized seizure: Subjects enrolled from prior study N01254 with a diagnosis of PGS at N01254 study entry

confidential information and ucb property

This document cannot be used to support any marketing authorization application and any extensions or variations thereof.

3. Unverricht-Lundborg disease: Subjects enrolled from prior studies N01187 and N01236

The Efficacy Population will consist of all subjects who took at least 1 dose of study medication and have at least 1 seizure diary during the Evaluation Period.

The Safety Population will consist of all subjects who took at least 1 dose of study medication.

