13.1.3 Statistical Evaluation

- General considerations:

Summary statistics will consist of frequency tables for categorical variables and descriptive statistics (number of available observations, mean, median, standard deviation, minimum, maximum, 25th and 75th percentiles) for continuous variables.

The periods considered are:

- Evaluation Period (V1 until the last Evaluation Visit).
- Down-Titration Period.
- Post-treatment Period.

Efficacy summaries will be created separately for the POS and PGS subpopulations within the efficacy population, and safety summaries will be created for the safety population and separately for the POS, PGS, and ULD subpopulations within the safety population.

- Baseline:

Baseline, whether efficacy or safety, will always refer to the original prior study pretreatment Baseline value. Baselines created and validated, as part of the prior study SAPs, will be copied and used by this study for all change from Baseline analyses.

- Study entry/disposition:

Subjects will be sufficiently described to enable a clear understanding of the populations and subpopulations and relevant demographics, disease, medical history, current treatment(s), as well as disposition. Historical and Baseline data will be copied from the prior study as required by the SAP.

- Seizure efficacy variables:

Analyses will be based upon the Efficacy Population. Summaries will be over the entire Evaluation Period and by 3-month periods over the Evaluation Period. The ULD subpopulation seizure diary data will not be summarized.

This document cannot be used to support any marketing authorization application and any extensions or variations thereof.

- QOLIE-31-P and EQ-5D efficacy variables:

Analyses will be based upon the Efficacy Population and summarized by data collection scheduled visits and for the last Evaluation Period assessment during the first 2 years. Data collected after year 2 are not planned to be summarized. The ULD subpopulation QOLIE-31-P and EQ-5D data will not be summarized.

- Pharmacoeconomic variables:

Analyses will be based upon the Efficacy Population and summarized by 3-month periods. Data collected after year 2 are not planned to be summarized. The ULD subpopulation pharmacoeconomic data will not be summarized.

- Safety variables:

Analyses will be based upon the Safety Population. Summary tables will be presented over the Evaluation Period by time windows, by periods, and by categories of total duration of exposure.

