2.4 Determination of Sample Size

No sample size calculation was done. Sample size was dependent upon recruitment into and completion of preceding studies. At the time of development of this SAP amendment 1, the enrollment into this study has been completed; a total of 859 subjects were enrolled into N01125 including 6 subjects entering the study from N01315.

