11 SAFETY ANALYSES

Safety is assessed with AEs, laboratory tests (blood chemistry, hematology, urinalysis, and pregnancy test), vital signs, body weight, ECGs, physical examination, neurological examination, mental status, and psychiatric status. Summary tables will be provided for AEs; blood chemistry, hematology, and urinalysis; vital signs; body weight; and ECGs. No summary tables will be provided for pregnancy testing, physical examination, neurological examination, mental status, or psychiatric status.

All safety summaries will be based on the Safety Analysis Set.

For subjects entering from N01315, their ongoing AEs will be transferred into N01125, and their safety assessments will be provided in subject data listings only, no summaries will be presented.

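### TEAEs, SAEs and deaths in the six subjects from N01315 enter no incidence table, because the SAP's Safety Analysis Set is narrower than the protocol's Safety Population and no reason is given

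*SAP*

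**What the plan says.** **Protocol.** Section 13.1.1 states: "The Safety Population will consist of all subjects who took at least 1 dose of study medication". Section 13.1.3 says that "safety summaries will be created for the safety population and separately for the POS, PGS, and ULD subpopulations within the safety population". Section 13 opens with a specific rule for the group in question: "Statistical analyses of data for subjects transferring from N01315 will be handled as described in the SAP".

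**SAP.** Section 3.5.1 takes dosed subjects as the Safety Analysis Set, "but not including subjects entering the study from N01315". It also defines a Modified Safety Analysis Set that puts those subjects back, for this use: "Demographic, ongoing medication and safety assessment listings will be provided based on the Modified Safety Analysis Set". Section 5.1 adds one overall disposition summary on the modified set. Section 11 states: "All safety summaries will be based on the Safety Analysis Set". For subjects from N01315 it adds that "their safety assessments will be provided in subject data listings only, no summaries will be presented". The overall AE summary in 11.2.2, which covers TEAEs, SAEs and deaths, is specified on the Safety Analysis Set.

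**Numbers.** Section 2.4 reports that "a total of 859 subjects were enrolled into N01125 including 6 subjects entering the study from N01315".

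**The concern.** Long-term safety is the primary objective, and the protocol summary states it for all subjects. The study is single-arm and purely descriptive, so the safety counts are the result. A reader who knows the protocol's definition will take the Safety Analysis Set to mean everyone who was dosed. It does not.

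The protocol names N01315 subjects as outside the efficacy and exploratory objectives (6.2, 6.3) and outside the efficacy and pharmacoeconomic variables (Section 4). It does not remove them from the primary safety objective. Its only safety exception for them concerns assessments limited to the first 2 years, and TEAE and SAE occurrence are not limited in that way.

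These subjects had their last N01315 visit and first N01125 visit at the same time. A death or rare SAE after that point would be found by someone reading the listings, but not by someone reading the incidence tables.

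**Working it through.** **1. Which outputs include the six subjects**

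| Output | Set used | N01315 subjects included? |
|---|---|---|
| Overall AE summary, including deaths (SAP 11.2.2) | Safety Analysis Set | No |
| TEAE, SAE and discontinuation-due-to-TEAE incidence (SAP 11.2.2) | Safety Analysis Set (SAP 11) | No |
| Disposition with reason, all enrolled (SAP 5.1) | All who consented | Yes |
| Disposition, modified set (SAP 5.1) | Modified Safety Analysis Set | Yes |
| Safety listings (SAP 3.5.1) | Modified Safety Analysis Set | Yes |

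Adverse event is one of the discontinuation categories in SAP 5.1. Withdrawal due to AE is therefore tabulated with these subjects included, though not by system organ class or preferred term. TEAEs, SAEs and deaths are not.

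**2. Is there a data obstacle to counting them?**
SAP 11.3 and 11.4 say that the prior-study baseline of these subjects is not carried over or presented. That rules out change-from-baseline tables. It does not affect AE counts: under SAP 11.2.1 a TEAE needs only an onset on or after the first BRV dose, and under 3.2.1 that means the first dose in N01125. Events still ongoing from N01315 are transferred (SAP 11). Those with onset before the first N01125 dose fall under pre-study AEs.

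**3. How large the effect can be**
There is no sample size, power or alpha to reproduce. The 859 is an enrolment count, inside the planned 500-1000. The documents do not give the number dosed, so assume that all 859 were dosed.

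- Denominator after exclusion: 859 − 6 = 853. Share excluded: 6/859 = 0.70%.
- If k of the 853 and j of the 6 have an event, adding the six changes the incidence by (k + j)/859 − k/853 = (6/859) × (j/6 − k/853). The bracket lies between −1 and 1, so the change cannot exceed 6/859 = 0.70 percentage points in either direction.
- One event: 1/859 = 0.12 points.

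| k of 853 (assumed) | Without the six | With the six: j = 0 | j = 1 | j = 6 |
|---|---|---|---|---|
| 0 | 0.00% | 0.00% | 0.12% | 0.70% |
| 9 | 1.06% | 1.05% | 1.16% | 1.75% |
| 725 | 84.99% | 84.40% | 84.52% | 85.10% |

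- One-sided 95% upper bound for an event never seen, 1 − 0.05^(1/n): 0.351% at n = 853 and 0.348% at n = 859.
- Chance that at least one of the six has a given event, 1 − (1 − p)^6, for assumed per-subject risks p: 3.0% at p = 0.5%, 5.9% at p = 1%, 46.9% at p = 10%.

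For common events nothing visible changes. For an outcome otherwise unseen, the tables could show 0 where the study had 1.

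**The case against.** **Delegation.** A reader might infer that the SAP breaks the protocol. The documents do not support that. Protocol Section 13 hands the analysis of N01315 subjects to the SAP, and this specific rule governs the general definition in 13.1.1. The three protocol subpopulations (POS, PGS, ULD) contain no N01315 subjects either. The SAP discloses its choice in 3.5.1, 11, 11.3, 11.4 and Section 14. This objection stands in full against any claim of contradiction. It does not supply the missing reason for the exclusion, which neither 3.5.1 nor Section 14 gives.

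**Scope.** A reader might also infer that all three primary safety variables omit these subjects, or that their data are lost. Neither holds. Withdrawal due to AE reaches the disposition summaries, the listings carry the rest, and protocol 12.4.2 requires every SAE to be reported to the sponsor within 24 hours. For six people a listing may tell more than a shift of 0.12 points.

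**Pooling.** Moving every safety table to the modified set would bring its own problems. These subjects come from another long-term study, and their clock would restart at Day 1 of N01125 beside subjects whose transition visits were at Week 12 or 16 of a double-blind study (SAP 3.2.3). Subjects from the double-blind studies may also have had BRV before entry, so this does not forbid pooling. It does weigh against moving the exposure tables. Tables by indication are awkward too: protocol 5.6 lists N01315 as a source of both partial-onset and generalized epilepsy, while the Statement that closes 5.6 and SAP 2.3 describe POS only. This objection limits the remedy. It does not touch a simple count of subjects with an SAE or who died.

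**Conclusion.** The point holds as a reporting gap of low severity. The SAP uses almost the same name as the protocol for a narrower set and gives no reason. TEAEs, SAEs and deaths in six treated subjects therefore reach no incidence table, although counting them needs only a first-dose date and an onset date.

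The effect is at most about 0.7 percentage points on any incidence, and about 0.12 points per event. This assumes that all 859 enrolled subjects, including the six, were dosed. The documents report no death or SAE in this group, so the consequence for a rare outcome is a possibility and not an observed error. No conclusion about common events depends on it.

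**What to change.** 1. In SAP 11.2.2, keep the current tables and add the overall AE summary (any TEAE, treatment-emergent SAE, TEAE leading to permanent discontinuation, death) on the existing Modified Safety Analysis Set.
2. Footnote that table to say that exposure of the six subjects during N01315 is not counted.
3. In SAP 3.5.1, give the reason for excluding N01315 subjects from the Safety Analysis Set. Adjust the two sentences in SAP 11 that tie all safety summaries to that set and rule out summaries for N01315 subjects, so that they allow the added table.
4. Leave exposure, subgroup and baseline-dependent tables on the current Safety Analysis Set.

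The cost is one extra table, a footnote and a few sentences of SAP text. The set is already defined, and no new data need to be collected.

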3.5.2 Efficacy Analysis Sets

Efficacy Analysis Sets will consist of all subjects who took at least 1 dose of study drug and have at least 1 seizure diary day during the Evaluation Period. Separate Efficacy Analysis Sets are defined for subjects with focal epilepsy from N01114, N01252, and N01254 and subjects with generalized epilepsy from N01254.

A subject will be excluded from the Efficacy Analysis Set for POS or PGS if either they did not receive at least 1 dose of BRV, or the clinical database indicates that the daily seizure diary was not completed for any days on or after the first dose of BRV and on or prior to the end date of the Evaluation Period (see Section 8).

Seizure outcomes will be summarized for either the Efficacy Analysis Set for POS or the Efficacy Analysis Set for PGS. Summaries of epilepsy history, QOLIE-31-P, and EQ-5D will be provided for the Efficacy Analysis Sets for both POS and PGS. No summaries of these outcomes will be provided for ULD subjects or subjects entering the study from N01315, but these data will only be provided in subject data listings.

3.6 Treatment Assignment and Treatment Groups

This is an uncontrolled study in which all subjects receive BRV in doses that are optimally adjusted for each subject. Generally, statistical summaries will present all subjects combined as a single treatment arm unless otherwise indicated.

3.7 Coding dictionaries

Medical history and AEs will be coded using the Medical Dictionary for Regulatory Activities (MedDRA). Medications will be coded using the World Health Organization Drug Reference List (WHO-DRL). Prior and concomitant medical procedures will not be coded.

3.8 Definitions of study-specific derived variables

3.8.1 Calculation of seizure frequency/days

3.8.1.1 Initial seizure data processing

Each seizure code in the clinical database will be mapped to exactly 1 of the following codes based on the 1981 International League Against Epilepsy (ILAE) classification: I, IA, IA1, IA2, IA3, IA4, IB, IB1, IB2, IC, II, IIA, IIB, IIC, IID, IIE, IIF, or III.

With regard to cluster seizures, investigator sites are to report the number of cluster episodes rather than reporting the estimated number of individual seizures. Therefore, no imputation will be applied for the seizure counts corresponding to reports of cluster seizures.

3.8.1.2 Calculation of adjusted seizure frequency

The following derivations apply only to subjects with Partial Onset Seizures.

Baseline POS frequency for seizure types I, IA, IB, IC, and for all seizure types (I+II+III) will be obtained from the Baseline Period of the previous double-blind study.

The total number of seizures for seizure types I, IA, IB, and IC, and the total number of seizures for all seizure types (I+II+III) will be calculated overall, by 3-month time intervals, and over the cohort interval for each exposure duration cohort. All seizure diary on or after the date of first dose of BRV and prior to or on the date of last dose of BRV will be considered for these calculations.

Twenty-eight day adjusted seizure frequency for seizure types I, IA, IB, and IC, and for all seizure types (I+II+III) will be calculated overall, within each 3-month time interval, and over each exposure duration cohort interval by dividing the total number of seizures for each seizure type by the number of days for which the diary was completed overall, within each 3-month interval, and within each exposure duration cohort interval, and multiplying the resulting value by 28.

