13.1.2.2 Efficacy Variables

- Secondary efficacy variables

For subjects with focal-onset epilepsy:

- Partial onset seizure (type I) frequency per 28 days during the Evaluation Period.
- Percent reduction in POS (type I) frequency per 28 days from Baseline of the previous study to the Evaluation Period.
- Responder rate for POS (type I) frequency over the Evaluation Period. A responder is defined as a subject with a $\geq 50\%$ reduction in seizure frequency from the Baseline Period of the previous study.

confidential information and ucb property

This document cannot be used to support any marketing authorization application and any extensions or variations thereof.

No secondary efficacy variables are defined for subjects with generalized epilepsy or subjects with ULD.

- Other efficacy variables

For subjects with focal-onset epilepsy:

- Percentage of subjects continuously seizure free for all seizure types (I+II+III) for at least 6 months and at least 12 months during the Evaluation Period.

For subjects with generalized epilepsy:

- Generalized (type II) seizure days per 28 days during the Evaluation Period.
- Percent reduction in generalized (type II) seizure days per 28 days from Baseline of the previous study to the Evaluation Period.
- Responder rate for generalized (type II) seizure days over the Evaluation Period. A responder is defined as a subject with a $\geq 50\%$ reduction in seizure days from the Baseline Period of the previous study.
- Percentage of subjects continuously seizure free for all seizure types (I+II+III) for at least 6 months and at least 12 months during the Evaluation Period.

The following will be evaluated separately for subjects with focal-onset epilepsy and subjects with generalized epilepsy:

- Change in QOLIE-31-P scores from Baseline of the previous study to each assessment for the first 2 years and to the last Evaluation Period assessment during the first 2 years.
- EQ-5D Questionnaire response for each assessment for the first 2 years for the Evaluation Period and for the last assessment during the first 2 years of the Evaluation Period.

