2.2.2 Efficacy variables

2.2.2.1 Secondary efficacy variables

For subjects with focal-onset epilepsy:

- POS (type I) frequency per 28 days during the Evaluation Period
- Percent reduction in POS (type I) frequency per 28 days from Baseline of the previous study to the Evaluation Period
- Responder rate for POS (type I) frequency over the Evaluation Period. A responder is defined as a subject with a $\geq 50\%$ reduction in seizure frequency from the Baseline Period of the previous study.

No secondary efficacy variables are defined for subjects with generalized epilepsy or subjects with ULD or subjects entering the study from N01315.

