2.2.2.2 Other efficacy variables

For subjects with focal-onset epilepsy:

- Percentage of subjects continuously seizure-free for all seizure types (I+II+III) for at least 6 months and at least 12 months during the Evaluation Period

For subjects with generalized epilepsy:

- Generalized (type II) seizure days per 28 days during the Evaluation Period
- Percent reduction in generalized (type II) seizure days per 28 days from Baseline of the previous study to the Evaluation Period
- Responder rate for generalized (type II) seizure days over the Evaluation Period. A responder is defined as a subject with a $\geq 50\%$ reduction in seizure days from the Baseline Period of the previous study.
- Percentage of subjects continuously seizure-free for all seizure types (I+II+III) for at least 6 months and at least 12 months during the Evaluation Period

The following will be evaluated separately for subjects with focal-onset epilepsy and subjects with generalized epilepsy:

- Change in Patient Weighted Quality of Life in Epilepsy Questionnaire (QOLIE-31-P) scores from Baseline of the previous study to each assessment for the first 2 years and to the last Evaluation Period assessment during the first 2 years
- EuroQol 5 Dimensions (EQ-5D) questionnaire response for each assessment for the first 2 years for the Evaluation Period and for the last assessment during the first 2 years of the Evaluation Period

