3.2 Analysis time points

3.2.1 First and last dose of BRV

Unless otherwise noted, all references to the first dose of BRV in this SAP refer to the first dose of BRV during N01125 (ie, not the first dose of BRV from the previous study in which subjects participated in prior to N01125). Unless otherwise noted, all references to the last known dose of BRV in this SAP refer to the last dose of BRV taken across any study periods (ie, the last dose of BRV across both the Evaluation and Down-Titration Periods).

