3.2.4 Study periods

The study is divided into 3 periods: Evaluation Period, Down-Titration Period, and Post-Treatment Period. A subject is classified as “discontinued” if the subject has a termination case report form (CRF) or has an early discontinuation visit (EDV). A subject is classified as “completed” if this subject completes the full extent of the study as defined in the protocol at database lock.

A “discontinued” subject can be potentially slotted into the 3 periods of the study. The following algorithms will be used to slot the subject appropriately into the Evaluation Period, Down-Titration Period, and Post-Treatment Period.

- For Evaluation Period, the start date is the date of first dose of BRV, and the following algorithm is used to determine the end date:
 - If the subject enters the Down-Titration Period, then the date of EDV is the end date;
 - If the subject does not enter the Down-Titration Period but meets 1 of the following criteria, the Evaluation Period ends on date of last dose of BRV,
 - Without an EDV but having a termination CRF,
 - With an EDV and having a termination CRF,
 - With an EDV and the date of EDV prior to the database lock date and having no termination CRF.
- A subject is considered entering Down-Titration Period only if the subject has an EDV and at least 1 dose of study drug after the date of EDV, the start date of Down-Titration Period is set as 1 day after the date of EDV, and the Down-Titration Period ends on date of last dose of BRV. A subject without an EDV but having a termination CRF or with an EDV but without any dosing of study drug after the EDV will not have the Down-Titration Period, and no artificial Down-Titration Period will be created for analysis.
- A subject is considered entering the Post-Treatment Period if the subject has at least 1 contact (scheduled visit, unscheduled visit, or telephone contact) after the date of last dose of BRV. The Post-Treatment Period starts 1 day after date of last dose of BRV irrespective of entering the Down-Titration Period, and there is no end date.

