A “completed” subject can potentially have Evaluation Period, Down-Titration Period, and Post-Treatment Period. At the time of study termination by the Sponsor, subjects will discontinue the study drug following the down titration process or will be converted without titration to commercial BRV where available; alternatively, subjects may be initiated without down-titration in a managed access program, named patient program, compassionate use program, or similar type of access program as allowed per country specific requirements in addition to legal and regulatory guidelines.

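### Seizure outcomes are defined over the Evaluation Period but computed to the last dose, so the overall results can include Down-Titration days, and the SAP does not declare the change

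*SAP*

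**What the plan says.** **Defined window.** Protocol 13.1.2.2 lists "Partial onset seizure (type I) frequency per 28 days during the Evaluation Period", and ties percent reduction, responder rate, generalized seizure days and seizure freedom to the same period. Protocol 13.1.3 treats Down-Titration as a separate period and says of the seizure variables: "Summaries will be over the entire Evaluation Period and by 3-month periods over the Evaluation Period". SAP 2.2.2.1 repeats the definition ("POS (type I) frequency per 28 days during the Evaluation Period"), and SAP 2.2.2.2 does so for seizure freedom: "Percentage of subjects continuously seizure-free for all seizure types (I+II+III) for at least 6 months and at least 12 months during the Evaluation Period".

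**End of that window.** SAP 3.2.4, for discontinued subjects: "If the subject enters the Down-Titration Period, then the date of EDV is the end date". A completed "subject can potentially have Evaluation Period, Down-Titration Period, and Post-Treatment Period", but the end-date algorithm in that section is written for discontinued subjects only.

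**Computed window.** SAP 3.8.1.2 takes diary data "on or after the date of first dose of BRV and prior to or on the date of last dose of BRV", and 3.8.1.3 uses the same data for generalized seizure days. SAP 3.2.1 explains last dose as "the last dose of BRV across both the Evaluation and Down-Titration Periods". Sections 8.1.1 to 8.1.3 report over the On Treatment Period, which 3.2.7 sets as first to last dose, and 8.2.2.1 to 8.2.2.3 follow the same method. Section 8.2.1.1, and 8.2.2.4 by reference, assesses seizure freedom over the time treated with BRV.

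**The concern.** For a subject who tapers after the EDV, the two windows differ by the whole taper. The analysis sections therefore deliver the study's only secondary efficacy variables, and seizure freedom, over a window that neither the protocol nor SAP 2.2.2 names. The SAP presents its On Treatment window openly, but does not call it a change. Its amendment section (14) does not mention it, and no Evaluation Period version is planned.

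A reader of the report who relies on the stated definitions would take the results as describing stable adjunctive treatment. The overall results would in fact mix in days when the drug was being withdrawn. Two gaps add to this: SAP 3.2.5 admits subjects to efficacy intervals by an end date that it does not define, and completed subjects who taper have no Evaluation Period end date.

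**Working it through.** The documents give no figure to reproduce. The check compares the windows and then works out what the extra days can do.

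**1. Who is affected.** A discontinued subject with no dose after the EDV has an Evaluation Period that ends at the last dose (SAP 3.2.4), so the windows coincide. Completers who move to commercial BRV or an access programme without tapering are not affected either. That leaves subjects who taper. For frequency, seizure days and responder status, the taper diary must also come back. The card is issued at the EDV (Protocol 10.3.5) and collected at the Final Visit (10.3.7), which Protocol 8.3 asks for only as a preference. Missing days are ignored (13.3.1).

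**2. Taper length.** The documents' own steps (50 mg/day each week, last week at 20 mg/day) imply at least 7, 14, 21 or 28 days from 50, 100, 150 or 200 mg/day.

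**3. Percent reduction for one subject.** Let T = total days to last dose, d = taper days, m = taper rate divided by baseline rate, and f = share of the taper diary retrieved. Assume a 55% reduction before taper.

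Overall reduction = 1 − [(T − d) × 0.45 + f × d × m] / [(T − d) + f × d]

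Example with d = 14, T = 180, m = 1, f = 1: 1 − (166 × 0.45 + 14)/180 = 1 − 88.7/180 = 50.7%, a fall of 4.3 points.

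| Taper (m = 1, f = 1) | T = 180 | T = 360 | T = 720 | T = 1800 |
|---|---|---|---|---|
| 7 days | 52.9% | 53.9% | 54.5% | 54.8% |
| 14 days | 50.7% | 52.9% | 53.9% | 54.6% |

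The 7-day falls are half the 14-day falls: 2.1 against 4.3 points at 180 days, and 0.5 against 1.1 at 720.

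Sensitivity to the unknowns (d = 14, T = 180):
- Taper rate, full diary: 56.9% at m = 0.2; 55.0% at m = 0.45 (no change); 50.7% at m = 1; 46.8% at m = 1.5. The shift can go either way.
- Diary retrieval at m = 1: 55.0% if none, 52.8% if half, 50.7% if all.

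**4. Responder status.** With m = 1 and f = 1, a responder over the Evaluation Period is lost only if the true reduction r satisfies 0.50 ≤ r < 0.50/(1 − d/T). For d = 14 the upper limit is 54.2% at 180 days, 52.0% at 360 and 51.0% at 720.

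**5. Seizure freedom.** Every interval inside the Evaluation Period also lies inside the On Treatment window. The overall count can therefore only stay the same or rise.

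Section 8.2.1.1 accepts 90% diary completion, which allows 18 missing days in 180 and 36 in 360. If no taper diary comes back, completion of an interval of L days that includes the whole taper is (L − d)/L:

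| Taper | L = 180 | L = 360 |
|---|---|---|
| 7 days | 96.1% | 98.1% |
| 14 days | 92.2% | 96.1% |
| 21 days | 88.3% | 94.2% |
| 28 days | 84.4% | 92.2% |

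With a 14-day taper, a subject with a seizure-free run of 166 to 179 days at the EDV can count as 6-month seizure-free, provided no seizure is reported in the taper days used. The corresponding run for 12 months is 346 to 359 days. The case matters only if the subject has no earlier qualifying run. At 166 days with no taper diary, at most 18 − 14 = 4 other diary days may be missing.

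**6. Interval and cohort results.** A cohort interval stops at the cohort cut (8.2.1.1: end of Month 6 for the 6-month cohort). With a 14-day taper, taper days enter the 6-month interval only if the last dose falls on days 180 to 193.

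Three-month intervals require the end date to reach the last day of the interval (3.2.5). If end date means last dose and last doses fall evenly over 90 days (assumed), a 14-day taper puts on average (14 + 13 + … + 1)/90 = 105/90 = 1.2 taper days into a counted interval. If it means the end of the Evaluation Period, the figure is zero.

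**The case against.** The best defence is that the applied rule is clear. SAP 3.8.1.2, 3.2.1, 3.2.7 and 8.1 agree on first to last dose, and the second paragraph of 4.2 says the same for subjects who discontinue. Protocol section 13 calls itself a general description and leaves detail to the SAP. Efficacy is descriptive, uncontrolled and not the primary objective, so no test or decision turns on the window. On this view only a sentence is missing.

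Much of this stands. Two programmers would probably cut the overall data at the same date. Requiring an Evaluation Period diary day for efficacy-set membership (3.5.2) does not by itself conflict with a longer summary window. But the period over which a variable is measured is part of its definition, not a detail. The SAP also restates the protocol's definition in 2.2.2 and then computes something else.

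A reader might infer more than the documents support:
- **That all efficacy results are contaminated.** Step 6 shows that cohort-interval and three-month results are largely protected.
- **That the distortion is large.** A 28-day taper within 90 total days would give 37.9% under the same assumptions, but it means leaving from 200 mg/day. SAP 2.3 puts starting doses from the double-blind studies at no more than 100 mg/day and the cap at 150 mg/day before Amendment 25, and all subjects had completed the Entry Visit by Amendment 26. That case is implausible.
- **That the SAP window flatters the drug throughout.** Only overall seizure freedom has a fixed direction.

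A further objection concerns the remedy, and it is right. Cutting the diary at the EDV while leaving cohort membership on exposure would keep a subject with 166 Evaluation and 14 taper days in the 6-month cohort with no way to qualify as 6-month seizure-free. The fix has to change both.

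**Conclusion.** The inconsistency is real and should be resolved, but its reach is limited. It affects tapering subjects only, and mainly the whole-period results.

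For one subject with a 14-day taper, the overall percent reduction falls about 4.3 points at 180 total days and 1.1 at 720; a 7-day taper gives about half of this. These figures assume a 55% reduction before taper, a return to baseline rate in taper and full diary retrieval. The documents establish none of these, and a different taper rate could reverse the sign. The group effect cannot be computed, because the documents do not give the number of tapering subjects, their exposure or their taper seizure rates.

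For overall seizure freedom the direction is certain, upward or none, but the group that could be added is narrow. The documents do not support a conclusion that efficacy is materially overstated.

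**What to change.** **Preferred.**
- For the overall results, cut seizure diary data at the Evaluation Period end date of SAP 3.2.4 (in 3.8.1.2, 3.8.1.3, 8.1.1 to 8.1.3, 8.2.1.1 and 8.2.2).
- In 8.2.1.1, require the seizure-free interval to lie within the Evaluation Period, and apply the rule that counts short-duration subjects as failures to Evaluation Period days.
- Define end date in 3.2.5 for efficacy intervals.
- Add an Evaluation Period end date for completed subjects who taper.
- For efficacy summaries by cohort, base membership on Evaluation Period days too, so that denominator and window match. A footnote is not enough.

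**Alternative.** Keep the On Treatment window, declare it as a change from the protocol and SAP 2.2.2, and report the overall Evaluation Period result beside it.

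**Cost.** SAP wording and modest reprogramming. The end date is already derived for discontinued subjects, and no new data are needed. The change concerns the analysis only and alters no dose or taper rule.
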